6.1.3 Hepatic adverse events

Hepatic AEs including elevated liver function tests (LFTs) and infrequently hepatitis have been observed following treatment with nivolumab. Most cases were low or moderate grade. Higher grade hepatic AEs were managed with corticosteroids and in all cases the events resolved. Early recognition and treatment of elevated LFTs and hepatitis are critical to its management. Patients should be advised to seek medical evaluation if they notice jaundice (yellow appearance of skin or sclera) or if they develop bruising, bleeding, or right-sided abdominal pain. Physicians should monitor LFTs prior to each nivolumab treatment. As LFT abnormalities are common in patients with CLL, it is important that an evaluation/work-up distinguish between non-drug-related causes (eg, infection, progression of disease, concomitant medications, alcohol) and a possible drug- related AE as the management is quite different. If non-inflammatory cause is identified, treat accordingly and continue nivolumab therapy. Consider imaging for obstruction.

Grade of LFT abnormality	Management	Follow-up

Grade 1
 
AST or ALT > ULN - 2.5 x ULN and/or T. bili > ULN - 1.5 x ULN
	
 ▪ Continue nivolumab 	
 ▪ Continue LFT monitoring per protocol 
If worsens:
 
 ▪ Treat as Grade 2 or 3-4

Grade 2
 
AST or ALT > 2.5 to ≤ 5 x ULN
	
 ▪ Delay nivolumab (Note: Discontinue nivolumab if 	
If returns to baseline:
 
 ▪ Resume routine monitoring,

and/or T. bili > 1.5 to \leq 3 x ULN	concurrent AST or ALT > 3 x ULN and total bilirubin > 2 x ULN) 
 ▪ Monitor LFTs at least every 3 days 	resume nivolumab If elevations persist > 5-7 days or worsen: 
 ▪ Steroids: 0.5-1 mg/kg/day methylprednisolone or oral equivalent and when LFT returns to grade 1 or baseline, taper steroids over at least 1 month, and resume nivolumab ▪ consider prophylactic antibiotics for opportunistic infections
Grade 3-4 AST or ALT > 5 x ULN and /or T.bili >3 x ULN	
 ▪ Discontinue Nivolumab (Note: Nivolumab may be delayed rather than discontinued if AST/ALT \leq 8 x ULN and T.bili \leq 5 x ULN) ▪ Monitor LFTs every 1-2 days ▪ Steroids: 1-2 mg/kg/day methylprednisolone IV or IV equivalent (Note: Use 2 mg/kg/day dose for Grade 4 LFTs) methylprednisolone IV. ▪ Add prophylactic antibiotics for opportunistic infections ▪ Consult hepatologist or gastroenterologist 	If returns to grade 2: 
 ▪ Taper steroids over at least 1 month If does not improve in >3-5 days, worsens or rebounds: 
 ▪ Add mycophenolate mofetil ▪ If no response within an additional 3-5 days, consider other immunosuppressants

Patients on IV steroids may be switched to an equivalent dose of oral corticosteroids (e.g. prednisone) at start of tapering or earlier, once sustained clinical improvement is observed.

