6.0 DOSE DELAYS AND MODIFICATIONS

Patients who experience Grade 3 or 4 toxicity that can be clearly attributed to either nivolumab or to ibrutinib may continue treatment with the other agent while the causative agent is delayed until resolution of toxicity to grade ≤1 or baseline. In cases where Grade 3 or 4 toxicity cannot be attributed to a specific study drug, both study drugs should be held regardless of attribution of toxicity until the toxicity is resolved to grade ≤1 or baseline. Grade 3 or 4 nivolumab immune-related toxicities will generally result in discontinuation of nivolumab, leaving ibrutinib monotherapy.

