6.1.11 Criteria to Resume Treatment

Patients may resume treatment with study drug when the drug-related AE(s) resolve to Grade ≤1 or baseline value, with the following exceptions:

- Patients may resume treatment in the presence of Grade 2 fatigue
- Patients who have not experienced a Grade 3 drug-related skin AE may resume treatment in the presence of Grade 2 skin toxicity
- Patients with baseline Grade 1 AST/ALT or total bilirubin who require dose delays for reasons other than a 2-grade shift in AST/ALT or total bilirubin may resume treatment in the presence of Grade 2 AST/ALT OR total bilirubin
- Patients with combined Grade 2 AST/ALT AND total bilirubin values meeting discontinuation parameters (Discontinuation Section, Section 12.0) should have treatment permanently discontinued
- Drug-related pulmonary toxicity, diarrhea, or colitis, must have resolved to baseline before treatment is resumed
- Drug-related endocrinopathies adequately controlled with only physiologic hormone replacement may resume treatment

If the criteria to resume treatment are met, the subject should restart treatment at the next scheduled timepoint per protocol. However, if the treatment is delayed past the next scheduled timepoint per protocol, the next scheduled timepoint will be delayed until dosing resumes.

If treatment is delayed > 6 weeks, the subject must be permanently discontinued from study therapy, except as specified in discontinuation section.

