12.0 DISCONTINUATION OF STUDY TREATMENT

A patient's treatment with study drugs may be discontinued for any of the following reasons:

- Clinically significant progressive disease
- Adverse events that are not manageable with dose adjustments and/or optimal medical management, or that, in the opinion of the investigator, pose an unacceptable risk for the patient.
- Investigator decision
- Patient decision (e.g., withdrawal of consent)
- Study termination by Sponsor

Patients who experience toxicity that can be clearly attributed to either nivolumab or to ibrutinib may continue treatment with the other agent. If toxicity cannot be clearly attributed to a single agent, treatment with both agents should be discontinued. Patients who discontinue treatment for reasons other than progressive disease should remain on study and continue to have disease assessments per protocol.

Additional Discontinuation Criteria for Nivolumab

Treatment should be permanently discontinued for the following:

- Any Grade 2 drug-related uveitis or eye pain or blurred vision that does not respond to topical therapy and does not improve to Grade 1 severity within the re-treatment period OR requires systemic treatment
- Any Grade 3 non-skin, drug-related adverse event lasting > 7 days, with the following exceptions for drug-related laboratory abnormalities, uveitis, pneumonitis, bronchospasm, diarrhea, colitis, neurologic adverse event, hypersensitivity reactions, and infusion reactions

- Grade 3 drug-related uveitis, pneumonitis, bronchospasm, diarrhea, colitis, neurologic adverse event, hypersensitivity reaction, or infusion reaction of any duration requires discontinuation
- Grade 3 drug-related laboratory abnormalities do not require treatment discontinuation except those noted below:
 - Grade 3 drug-related thrombocytopenia > 7 days or associated with bleeding requires discontinuation
 - Any drug-related liver function test (LFT) abnormality that meets the following criteria require discontinuation:
 - AST or ALT > 8 x ULN
 - Total bilirubin > 5 x ULN
 - Concurrent AST or ALT > 3 x ULN and total bilirubin > 2 x ULN
- Any Grade 4 drug-related adverse event or laboratory abnormality, except for the following events which do not require discontinuation:
 - Isolated Grade 4 amylase or lipase abnormalities that are not associated with symptoms or clinical manifestations of pancreatitis and decrease to < Grade 4 within 1 week of onset.

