 - Isolated Grade 4 electrolyte imbalances/abnormalities that are not associated with clinical sequelae and are corrected with supplementation/appropriate management within 72 hours of their onset
- Any dosing interruption lasting > 6 weeks with the following exceptions:
 - Dosing interruptions to allow for prolonged steroid tapers to manage drug-related adverse events are allowed. Prior to re-initiating treatment in a subject with a dosing interruption lasting > 6 weeks, the Investigator must be consulted. Tumor assessments should continue as per protocol even if dosing is interrupted
 - Dosing interruptions > 6 weeks that occur for non-drug-related reasons may be allowed if approved by the Investigator. Prior to re-initiating treatment in a subject with a dosing interruption lasting > 6 weeks, the Investigator must be consulted. Tumor assessments should continue as per protocol even if dosing is interrupted
- Any adverse event, laboratory abnormality, or intercurrent illness which, in the judgment of the Investigator, presents a substantial clinical risk to the subject with continued nivolumab dosing

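### The Grade 3-4 liver row lets nivolumab be delayed in patients whom Section 12 requires to stop permanently for combined AST/ALT and bilirubin elevation

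*Combined protocol and SAP*

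**What the plan says.** Section 6.1.3 manages liver toxicity by grade.

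- **Grade 2 row** (AST/ALT above 2.5 to 5 and/or bilirubin above 1.5 to 3 x ULN): delay nivolumab, but discontinue for "concurrent AST or ALT > 3 x ULN and total bilirubin > 2 x ULN".
- **Grade 3-4 row**, entered at "AST or ALT > 5 x ULN and /or T.bili >3 x ULN": discontinue. The note then relaxes this: "Nivolumab may be delayed rather than discontinued if AST/ALT" does not exceed 8 x ULN and bilirubin does not exceed 5 x ULN. It has no concurrent-elevation condition.

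Section 12.0 requires permanent discontinuation of nivolumab for any drug-related liver test abnormality meeting one of three criteria: AST or ALT above 8 x ULN; total bilirubin above 5 x ULN; or "Concurrent AST or ALT > 3 x ULN and total bilirubin > 2 x ULN". These criteria are listed as exceptions to the rule that Grade 3 laboratory abnormalities do not require stopping, so they plainly reach Grade 3.

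Three other provisions bear on the point:

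- Section 6.0: "Grade 3 or 4 nivolumab immune-related toxicities will generally result in discontinuation of nivolumab".
- Section 6.1.11 gives the general restart rule, "Patients may resume treatment with study drug when the drug-related AE(s) resolve to Grade" 1 or lower or to baseline. Its hepatic bar on restarting covers "Patients with combined Grade 2 AST/ALT AND total bilirubin values meeting discontinuation parameters" and refers to Section 12.0.
- Section 12.0, on the 6-week limit for interruptions: "Dosing interruptions to allow for prolonged steroid tapers to manage drug-related adverse events are allowed".

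**The concern.** The note in the Grade 3-4 row reproduces two of Section 12's three limits and drops the third. Because the Grade 2 row keeps it, the stricter instruction within Section 6.1.3 falls on the milder patient. An investigator facing rising liver tests will go to the organ-specific table. Following it, and then the restart rule in Section 6.1.11, that investigator has written permission to hold and later rechallenge a patient with combined transaminase and bilirubin elevation whom Section 12 removes permanently. What is at stake is patient safety and consistent handling. The efficacy endpoints, the Bayesian toxicity boundaries and the planned summaries are untouched.

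**Working it through.** The plan states no figure to reproduce, so the check compares the rules. Let A be AST or ALT and B total bilirubin, both as multiples of ULN, for a drug-related abnormality.

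**Rules**

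- Grade 3-4 row (6.1.3): A > 5 or B > 3.
- Note permits delay: in the row, with A ≤ 8 and B ≤ 5.
- Section 12 concurrent criterion: A > 3 and B > 2.

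**Regions**

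- Conflict (delay permitted, discontinuation required): {3 < A ≤ 8, 2 < B ≤ 5} minus {3 < A ≤ 5, 2 < B ≤ 3}. Equivalently, {5 < A ≤ 8, 2 < B ≤ 5} together with {3 < A ≤ 8, 3 < B ≤ 5}.
- Agreement (delay permitted, Section 12 does not require stopping): {5 < A ≤ 8, B ≤ 2} or {A ≤ 3, 3 < B ≤ 5}. These are near-isolated elevations.

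**Worked cases**

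| A | B | Row in 6.1.3 | Section 6.1.3 | Section 12 |
|---|---|---|---|---|
| 4 | 2.5 | Grade 2 | discontinue | discontinue |
| 6 | 2.5 | Grade 3-4 | delay permitted | discontinue |
| 4 | 4 | Grade 3-4 | delay permitted | discontinue |
| 6 | 4 | Grade 3-4 | delay permitted | discontinue |
| 8 | 5 | Grade 3-4 | delay permitted | discontinue |
| 6 | 1.5 | Grade 3-4 | delay permitted | not required |
| 2 | 4 | Grade 3-4 | delay permitted | not required |

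**Grid check**, A from 0.5 to 8 and B from 0.5 to 5 in steps of 0.5:

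- All points: 16 × 10 = 160. Outside the row (A ≤ 5 and B ≤ 3): 10 × 6 = 60. Delay permitted: 160 − 60 = 100.
- Conflict: (6 × 6) + (4 × 4) = 52. Agreement: (6 × 4) + (6 × 4) = 48.
- With the concurrent criterion added to the note, conflict falls from 52 to 0.

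These counts describe the rules, not how often patients land there.

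**Does Section 6.1.11 catch the conflict cases?** Its bar is worded for combined Grade 2 values, that is 2.5 < A ≤ 5 with 1.5 < B ≤ 3. Every conflict point has A > 5 or B > 3, so none lies in that range. A finer grid, in steps of 0.1, also found none.

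**How many patients might reach the row?** Table 2.4.2.4-1 gives treatment-related Grade 3-4 hepatic events in the solid-tumour monotherapy study. Assuming those rates apply to this combination and all 72 patients are enrolled, with exact (Clopper-Pearson) 95% intervals:

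- 3 mg/kg: 2/54 = 3.70% (0.45% to 12.75%); × 72 = 2.7 patients (0.3 to 9.2).
- All doses: 4/306 = 1.31% (0.36% to 3.31%); × 72 = 0.9 patients (0.3 to 2.4).

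The table does not report concurrent elevation, so the number in conflict is an unknown subset of these and may be zero.

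**The case against.** The best defence is that Section 12 already covers this patient. It is mandatory, the note is only permissive, and the row's default is to stop. Discontinuing satisfies both texts, so anyone who also applies Section 12 acts correctly. Section 6.1.11 defers to Section 12 twice, which suggests that Section 12 governs permanent discontinuation. The follow-up column of the Grade 3-4 row has no instruction to resume, unlike several other rows. The row requires a hepatology or gastroenterology consult, restarting after more than 6 weeks requires consulting the investigator, and all nivolumab is given at one centre.

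Much of this is true and limits the harm, but it does not remove the conflict. No clause says which section prevails. The liver cross-reference in Section 6.1.11 is confined to combined Grade 2 values. Delaying rather than discontinuing means dosing is expected to continue, and the general restart rule supplies the route. Section 6.0 says only that such toxicities generally lead to stopping. The 6-week limit exempts steroid tapers, and this row prescribes one of at least a month. Consultation does not forbid rechallenge.

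Two points stand in part. With liver tests every 1-2 days, some recovering patients may pass through combined Grade 2 values still above 3 and 2 x ULN, where the Grade 2 note would apply. That is incidental protection. Also, the patient counts are indicative only, because they carry solid-tumour monotherapy rates over to a different combination and population and assume full enrolment.

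**Conclusion.** The concern holds. For drug-related AST/ALT above 5 to 8 with bilirubin above 2 to 5 x ULN, or AST/ALT above 3 to 8 with bilirubin above 3 to 5 x ULN, Section 6.1.3 permits a delay where Section 12.0 requires permanent discontinuation. This follows from the text alone and needs no outside assumption. It is a permission set against a mandate, but the permission applies to the sicker patient. The number affected is probably small and may be zero; the estimate of patients reaching the row rests on the monotherapy rates carrying over. The inconsistency should be corrected for safety, but it does not threaten the trial's design or analysis.

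**What to change.** Let Section 12.0 stand and align Section 6 with it.

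1. In the Grade 3-4 note of Section 6.1.3, after the bilirubin limit, add: *and there is no drug-related concurrent AST or ALT > 3 x ULN with total bilirubin > 2 x ULN*.
2. In the hepatic bar of Section 6.1.11, replace the restriction to combined Grade 2 values with *combined AST/ALT and total bilirubin values (any grade)*, keeping the reference to Section 12.0.

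Keep the term drug-related. Patients with Gilbert's disease may enrol with bilirubin up to 3 x ULN (Section 3.1), and their baseline bilirubin should not by itself count as a drug effect. The qualifier does not settle how to treat a drug-related ALT above 3 x ULN on top of a Gilbert's bilirubin already above 2 x ULN; Section 12 leaves that open too, and one clarifying sentence would help.

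The cost is two one-line edits. No tests are added, because the row already requires liver tests every 1-2 days. A few patients lose the option of nivolumab rechallenge, which Section 12 already denies them. Delay stays available for near-isolated elevations.

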6.1.4 Endocrine adverse events

Endocrinopathies have been observed following treatment with nivolumab. Most cases are low or moderate grade. The events have typically been identified through either routine periodic monitoring of specific laboratories (eg, TSH) or as part of a work-up for associated symptoms (eg, fatigue). Events may occur within weeks of beginning treatment but also have been noted to occur after many months (while still on treatment). More than one endocrine organ may be involved. Early recognition and treatment of endocrinopathies are critical to its management. Patients should be advised to seek medical evaluation if they notice new onset of fatigue, lightheadedness, or difficulty with vision or if baseline fatigue worsens. As fatigue is common in patients with CLL, it is important that an evaluation/work-up distinguish between non-drug- related causes (eg, progression of disease, anemia, concomitant medications, depression) and a possible drug-related AE as the management is quite different. The principal management of endocrinopathies is hormone replacement therapy.

Asymptomatic TSH elevation	
 Continue nivolumab If TSH < 0.5 x LLN, or TSH > 2 x ULN, or consistently out of range in 2 subsequent measurements: consider endocrinology consult 	
Symptomatic endocrinopathy	
 Evaluate endocrine function Consider pituitary scan 
Symptomatic with abnormal lab/pituitary scan:
 
 Delay nivolumab Steroids: 1-2 mg/kg/day methylprednisolone IV or PO equivalent Initiate appropriate hormone therapy 
No abnormal lab/pituitary MRI scan but symptoms persist:
 
 Repeat labs in 1-3 weeks / MRI in 1 month 	
If improves (with or without hormone replacement):
 
 Taper steroids over at least 1 month and consider prophylactic antibiotics for opportunistic infections Resume nivolumab Patients with adrenal insufficiency may need to continue steroids with mineralocorticoid component
Suspicion of adrenal crisis (e.g. severe dehydration, hypotension, shock out of proportion to current illness)	
 Delay or discontinue nivolumab Rule out sepsis Stress dose of IV steroids with mineralocorticoid activity IV fluids Consult endocrinologist If adrenal crisis ruled out, then treat as above for symptomatic endocrinopathy 	

Patients on IV steroids may be switched to an equivalent dose of oral corticosteroids (e.g. prednisone) at start of tapering or earlier, once sustained clinical improvement is observed.

6.1.5 Skin adverse events

Rash and pruritus are the most common skin AEs observed following treatment with nivolumab. The rash is typically focal with a maculopapular appearance occurring on the trunk, back, or extremities. Most cases have been low or moderate grade. In some cases, rash and pruritus resolved without intervention. Topical corticosteroids have been used for some cases of rash. Anti-histamines have been used for some cases of pruritus. More severe cases responded to systemic corticosteroids. Patients should be advised to seek medical evaluation if they notice new onset rash. Early consultation with a dermatology specialist and a biopsy should be considered if there is uncertainty as to the cause of the rash or if there is any unusual appearance or clinical feature associated with it. Other drugs which may cause rash should be considered in the differential and if possible discontinued.

Grade of Rash	Management	Follow-up
Grade 1-2 (Covering ≤ 30% of BSA)	
 Continue nivolumab Symptomatic therapy 	
If persists > 1-2 weeks or recurs:
 
 Consider skin biopsy

	(e.g. antihistamines, topical steroids)	
 Delay nivolumab Steroids: Consider 0.5-1.0 mg/kg/day methylprednisolone IV or oral equivalent. Once improving, taper steroids over at least 1 month, consider prophylactic antibiotics for opportunistic infections, and resume nivolumab 
If worsens:
 
 Treat as Grade 2 or 3-4
Grade 3-4 (Covering >30% BSA; Life threatening consequences)	
 Delay or discontinue nivolumab Consider skin biopsy Dermatology consult Steroids: 1-2 mg/kg/day IV methylprednisolone IV or IV equivalent 	
If improves to Grade 1:
 
 Taper steroids over at least 1 month and add prophylactic antibiotics for opportunistic infections Resume nivolumab

Patients on IV steroids may be switched to an equivalent dose of oral corticosteroids (e.g. prednisone) at start of tapering or earlier, once sustained clinical improvement is observed.

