6.1.9 Uveitis and Visual Complaints

Immune therapies have been uncommonly associated with visual complaints. Inflammation of components within the eye (eg, uveitis) is an uncommon but clinically important event. An ophthalmologist should evaluate visual complaints. Topical corticosteroids may be used to manage low grade events. Low-grade events that do not resolve and high-grade events should be managed with systemic corticosteroids.

6.1.10 Nivolumab administration should be delayed for the following:

- Any Grade ≥ 2 non-skin, drug-related AE, with the following exceptions:
 - Grade 2 drug-related fatigue or laboratory abnormalities do not require a treatment delay
- Any Grade 3 skin, drug-related AE
- Any Grade 3 drug-related laboratory abnormality, with the following exceptions for lymphopenia, leukopenia, AST, ALT, total bilirubin, or asymptomatic amylase or lipase:
 - Grade 3 lymphopenia or leukopenia does not require dose delay
 - If a subject has a baseline AST, ALT, or total bilirubin that is within normal limits, delay dosing for drug-related Grade ≥ 2 toxicity
 - If a subject has baseline AST, ALT, or total bilirubin within the Grade 1 toxicity range, delay dosing for drug-related Grade ≥ 3 toxicity
 - Asymptomatic amylase or lipase does not require dose delay

- Any AE, laboratory abnormality, or intercurrent illness which, in the judgment of the investigator, warrants delaying the dose of study medication

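### The Grade 3-4 rash row in 6.1.5 lets nivolumab restart after a Grade 4 rash, although Section 12.0 requires permanent discontinuation

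*Combined protocol and SAP*

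**What the plan says.** **Section 6.1.5 (Skin adverse events).** The last row of the rash table is labelled "Grade 3-4 (Covering >30% BSA; Life threatening consequences". Its management column begins with "Delay or discontinue nivolumab", followed by biopsy, a dermatology consult and intravenous steroids. Its follow-up column applies when the rash has improved to Grade 1: taper the steroids over at least a month with antibiotic cover, then restart nivolumab. Neither column separates Grade 3 from Grade 4.

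**Section 12.0 (Additional Discontinuation Criteria for Nivolumab).** The list of reasons for permanent discontinuation includes "Any Grade 4 drug-related adverse event or laboratory abnormality, except for the following events which do not require discontinuation". The exceptions that follow are isolated amylase or lipase abnormalities and isolated electrolyte abnormalities, each with conditions. The separate Grade 3 criterion in the same list is confined to non-skin events, so a Grade 3 rash alone does not trigger a permanent stop.

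**Section 6.1.10 (delay rules).** The skin bullet reads "Any Grade 3 skin, drug-related AE". It does not mention Grade 4.

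**Section 6.1.11 (resume rules).** The general rule is "Patients may resume treatment with study drug when the drug-related AE(s) resolve to Grade ≤1 or baseline value", with listed exceptions. It points to the discontinuation section in two places: combined liver-test values, and delays longer than six weeks.

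**The concern.** For a drug-related Grade 4 rash that later settles to Grade 1, the management table says that nivolumab may be delayed and then restarted, while the discontinuation section says it must stop for good. The table is what a clinician would naturally consult at the bedside, and its restart step carries no warning that it excludes the more severe of the two grades in its own label.

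What is at stake is re-exposure of a patient to the drug that caused a life-threatening reaction. The point concerns patient safety and consistency of conduct, not the efficacy analysis.

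**Working it through.** No sample size, power or error rate is involved. The check is a comparison of texts, followed by a sense of scale from the background data.

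**Step 1. Follow a drug-related Grade 4 rash through each rule.**

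| Place | What it gives for Grade 4 rash |
|---|---|
| 6.1.5, last row | Delay or stop; restart after improvement to Grade 1 and a steroid taper |
| 6.1.10, skin bullet | Silent (Grade 3 only) |
| 6.1.11 | May resume at Grade 1 or baseline; no bar for a previous Grade 4 event |
| 12.0, Grade 4 criterion | Permanent stop; skin not among the exceptions |

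The first and last lines cannot both be followed if the investigator takes the delay branch of the row.

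**Step 2. Repeat for Grade 3 rash.** The row allows delay and restart, 6.1.10 requires delay, and the Grade 3 criterion in Section 12.0 excludes skin. These agree. The inconsistency therefore arises only because Grade 4 shares the row with Grade 3.

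**Step 3. See whether the same problem occurs in the other tables.** Pneumonitis Grade 3-4 (6.1.1), diarrhea/colitis Grade 3-4 (6.1.2), creatinine Grade 4 (6.1.6), neurologic Grade 3-4 (6.1.7) and infusion reaction Grade 3-4 (5.1.4) all say to discontinue and give no restart step. The hepatic Grade 3-4 row (6.1.3) also says discontinue; its allowance for delay ends at AST/ALT 8 x ULN and bilirubin 5 x ULN, which are the Section 12.0 limits. Among the graded tables, the rash row is the one that attaches a restart to a Grade 4 label without such a limit.

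**Step 4. Look for a sentence that settles precedence.** Section 11.1.2(f) has one, but it concerns recording and reporting of adverse events. None addresses dosing.

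**Step 5. Scale.** Counts are the treatment-related Grade 3-4 columns of Table 2.4.2.4-1 (MDX1106-03). Limits are exact two-sided 95% (Clopper-Pearson); with zero events in n patients the upper limit is 1 − 0.025^(1/n).

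- Rash, all doses: 0/306; upper limit 1 − 0.025^(1/306) = 1.2%.
- Any skin event, all doses: 1/306 = 0.3%; interval 0.01% to 1.8%.
- Any skin event at this trial's dose of 3 mg/kg: 0/54; upper limit 1 − 0.025^(1/54) = 6.6%.

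These counts pool Grades 3 and 4, so the observed Grade 4 counts can be no higher. Section 2.4.3 also reports no drug-related Grade 4 or 5 events among 23 patients with Hodgkin's lymphoma given nivolumab alone; for 0/23 the upper limit is 14.8%. The documents give no Grade 4 rate for the combination with ibrutinib, so none of these figures is projected onto the 72 planned patients.

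**The case against.** The best defence is that the row can be read consistently with Section 12.0. It offers two actions for two grades. Section 6.1.10 assigns delay to Grade 3 skin events, Section 12.0 assigns permanent discontinuation to Grade 4, and a restart can only follow the delay branch because a discontinued drug is not resumed. Section 6.0 adds that immune-related Grade 3 or 4 toxicity generally leads to stopping nivolumab. All infusions are given at one centre (Section 9.0), and Appendix 3 reserves protocol decisions to its investigators, which limits divergent readings.

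Much of this stands. It shows the probable intent and keeps the point small. It does not remove the defect: the reader must combine three sections to learn that the row's restart step excludes one of the grades in its label, and the row itself does not say so.

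Two stronger readings are tempting, and the documents do not support them.

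- *A reader might infer that the general delay and resume rules contradict Section 12.0 for Grade 4 events at large.* They do not. The 6.1.10 bullet "Any Grade ≥ 2 non-skin, drug-related AE, with the following exceptions" is a threshold for holding drug and confers no right to restart. Section 6.1.11 is permissive, so an investigator who holds nivolumab and then stops it permanently breaches neither section. The delay sentence in 6.0 mainly says when the other agent may continue, and it covers both drugs. These rules layer with Section 12.0.
- *A reader might infer a second conflict for adrenal crisis.* The 6.1.4 row reads "Suspicion of adrenal crisis (e.g. severe dehydration, hypotension, shock out of proportion to current illness" and also offers delay or discontinuation. But it concerns suspicion only, gives no grade and contains no restart step; calling such an event Grade 4 would be the reader's own assumption. Section 6.1.11 says "Drug-related endocrinopathies adequately controlled with only physiologic hormone replacement may resume treatment", and whether that should hold after a Grade 4 event is a clinical choice the documents leave open.

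**Conclusion.** The point holds for one row. As written, the Grade 3-4 rash row permits nivolumab to be restarted after a life-threatening rash once it has improved to Grade 1, and Section 12.0 forbids this for any drug-related Grade 4 rash. The surrounding text indicates that Section 12.0 is meant to govern, so this is an imprecise table row and not an open question of policy.

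The conclusion assumes that the rash is attributed to study drug, since the Section 12.0 criterion is confined to drug-related events, and that the investigator chooses delay over discontinuation. The background data suggest that very few patients would reach this situation, with the caveat that they come from nivolumab alone in other diseases. The correction should be made because it guards against re-exposure after a life-threatening toxicity. It has no effect on the primary endpoint.

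**What to change.** Split the last row of the 6.1.5 table:

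- **Grade 3:** delay nivolumab; on improvement to Grade 1, taper steroids as now described and then resume.
- **Grade 4:** permanently discontinue nivolumab per Section 12.0; keep the steroid taper and antibiotic cover, with no resume step.

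Optionally, add one sentence to 6.1.11 stating that resumption is subject to the nivolumab criteria in Section 12.0. If it is added, the sponsor should decide separately how endocrinopathies controlled on hormone replacement are to be handled, because that sentence would otherwise settle the matter by default. Section 12.0 itself needs no change.

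The cost is one table row and at most one sentence in an amendment. No visits, tests or patients are added.
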